4.0 Test Schedule

Tests and procedures	Active Monitoring Phase			
	≤14 days prior to registration (baseline)	Every 30 days after the start of treatment (± 1 week)	End of treatment	Observation: 3 months after the completion of treatment (as defined per protocol) (± 1 week)
History and exam (including weight and bleeding assessment, see App. IV)	X	X ⁶		
ECOG PS	X	X		
Height	X			
Adverse event assessment	X	X		X
Hematology: • CBC • Platelets	X ¹	X	X ⁵	
INR	X ¹			
Chemistry: • SGOT (AST) or ALT • Creatinine	X ¹	X	X ⁵	
Selected concomitant meds (see CRF for this form)	X	X		
US, CT, MRI, or VQ scan to confirm acute lower extremity or upper extremity DVT, PE or splanchnic vein thrombosis	X			
Pregnancy test ²	X			
Patient Questionnaire Booklets ³ (App. VI, VII) • Mayo Blood Thinner Questionnaire • Bruising Question	X ⁴	X		
Patient Phone Call (including bleeding assessment, see App. IV and VIII)			X	X

1. ≤30 days prior to registration.
2. For women of childbearing potential only. Must be done ≤24 hours prior to randomization.
3. Patient questionnaire booklets **must** be used; copies are not acceptable for this submission.
4. Must be completed after registration and prior to treatment.
5. If feasible.
6. If it is not feasible for the patient to return to the enrolling center for the physical examination, a detailed history will be obtained by phone using a structured interview (see Appendix X).

5.0 Stratification Factors

- 5.1 Cancer stage: Residual (intact primary or metastatic) vs. no residual (no evidence of disease).
- 5.2 Risk: High risk vs. lower risk using validated Khorana score (see appendix III).

6.0 Registration/Randomization Procedures

6.1 Registration Procedures

- 6.11 To register a patient, access the ACCRU web page at [REDACTED] click on "Training Page" and enter the registration/randomization application. The registration/randomization application is available 24 hours a day, 7 days a week. Back up and/or system support contact information is available on the Web site. If unable to access the Web site, call the Academic and Community Cancer Research United (ACCRU) Registration Office at [REDACTED] between the hours of 8 a.m. and 4:30 p.m. Central Time (Monday through Friday).

The instructions for the registration/randomization application are available by using the Help button. Prior to initiation of protocol study intervention, this process must be completed in its entirety and an ACCRU subject ID number must be available as noted in the instructions. It is the responsibility of the individual and institution registering the patient to confirm the process has been successfully completed prior to release of the study agent. Patient registration via the registration/randomization application can be confirmed in any of the following ways:

- Contact the ACCRU Registration Office [REDACTED]. If the patient was fully registered, the ACCRU Registration Office staff can access the information from the centralized database and confirm the registration.
- Refer to "Instructions for Remote Registration" in section "Finding/Displaying Information about A Registered Subject."

- 6.12 Documentation of IRB approval must be on file in the Registration Office before an investigator may register any patients.

In addition to submitting initial IRB approval documents, ongoing IRB approval documentation must be on file (no less than annually) at the Registration Office [REDACTED]. If the necessary documentation is not submitted in advance of attempting patient registration, the registration will not be accepted and the patient may not be enrolled in the protocol until the situation is resolved.

When the study has been permanently closed to patient enrollment, submission of annual IRB approvals to the Registration Office is no longer necessary.

- 6.13 Prior to accepting the registration/randomization, the registration/randomization application will verify the following:
 - IRB approval at the registering institution
 - Patient eligibility
 - Existence of a signed consent form

- Existence of a signed authorization for use and disclosure of protected health information
- 6.14 Treatment cannot begin prior to registration and must begin ≤ 5 days after registration.
- 6.15 Pretreatment tests/procedures (see Section 4.0) must be completed within the guidelines specified on the test schedule.
- 6.16 All required baseline symptoms (see Section 10.3) must be documented and graded.
- 6.17 Treatment on this protocol must commence at an ACCRU institution under the supervision of a health care professional.
- 6.18 Study drug is available on site.
- 6.19 Patient questionnaire booklet is available on site; copies are not acceptable for this submission.
- 6.2 Randomization Procedures
- 6.21 The factors defined in Section 5.0, together with the registering membership, will be used as stratification factors.
- 6.22 After the patient has been registered into the study, the values of the stratification factors will be recorded, and the patient will be assigned to one of the following treatment groups using the Pocock and Simon dynamic allocation procedure which balances the marginal distributions of the stratification factors between the treatment groups (Pocock-Simon).
- Apixaban
 - Dalteparin

7.0 Protocol Treatment

7.1 Treatment Schedule - Use actual weight (Kg)

Arm	Agent	Dose Level	Frequency	Route
A	Apixaban*	10 mg	Twice daily days 1-7	Oral
		5 mg	Twice daily days 8-180	
B	Dalteparin*	200 IU/kg/day	Once daily for days 1- 30	Subcutaneous Injection**
		150 IU/kg/day	Once daily for days 31-180	

*If a dose of apixaban or dalteparin is not taken at the scheduled time, the dose should be taken as soon as possible on the same day and the prescribed dosing schedule should be resumed. The dose should not be doubled to make up for missed doses.

** The dosage will be calculated on the patient's current weight in kilograms, rounded to the nearest whole kilogram. The syringe dose will be chosen based on the weight adjusted calculation based on the table 7.11. The patient will be taught by on site nursing staff how to administer the medication, and also how to "waste" from each syringe such that the appropriate weight adjusted

dose is delivered.

7.11

Month 1: 200 IU/kg SQ daily

Body Weight (kg)	Dalteparin Dose (IU) once daily
≤ 40	7,500
41-56	10,000
57-68	12,500
69-82	15,000
83-94	18,000
95-107	10,000 & 10,000 = 20,000
108-120	18,000 & 5,000 = 23,000
121-133	15,000 & 10,000 = 25,000
134-147	18,000 & 10,000 = 28,000
148-160	15,000 & 15,000 = 30,000
≥161	200 IU/kg SQ daily

Months 2-6: 150 IU/kg SQ daily

Body Weight (kg)	Dalteparin Dose (IU) once daily
≤ 40	5,000
41-57	7,500
58-77	10,000
78-92	12,500
93-110	15,000
111-130	18,000
131-141	10,000 & 10,000 = 20,000
142-160	18,000 & 5,000 = 23,000
≥161	150 IU/kg SQ daily

- 7.12 **Dalteparin therapy is weight based dosing.** Monthly weights should be performed and communicated with the study coordinator. For patients experiencing more than 10% weight loss or gain, the dose of dalteparin will be adjusted to current body weight. Round according to table 7.11.
- 7.13 Scheduled visits should include a standardized assessment of the signs and symptoms of recurrent thromboembolism, bleeding episodes, and adverse reactions. Patients should be instructed to report to the clinic immediately (or call 911/go to the Emergency Room) if they had any bleeding, or symptoms of recurrent deep-vein thrombosis, pulmonary embolism, or both. Written patient education materials will be provided to each patient outlining signs and symptoms to watch for regarding VTE recurrences (appendix IX). All suspected episodes of recurrent thrombosis should be investigated with the use of objective

tests, according to pre-specified diagnostic algorithms.

7.2 Post protocol completion: Anticoagulation decision algorithm

7.21 Following the 6 months of protocol completion, a decision regarding anticoagulation continuation will be clinically determined. (31) Although cancer is associated with a high risk of recurrent venous thromboembolism, the rate of recurrence differs significantly by cancer type, stage of disease, and stage progression over time. For the following patient characteristics, we recommend continuing anticoagulation: patients with brain, lung, pancreatic, or ovarian cancer; myeloproliferative or myelodysplastic disorders; stage IV cancer; cancer stage progression; or leg paresis. Anticoagulation options could include: continued LMW heparin (dalteparin or enoxaparin), apixaban (or other oral novel direct factor inhibitors or warfarin).

For patients not meeting these specific criteria or if their presenting thrombus was limited to the calf (distal to and not including the popliteal vein), it is reasonable to discontinue anticoagulation therapy.

7.22 For surveillance purposes, participants will be contacted by telephone at 3 months post protocol completion to determine the incidence of thrombosis recurrence, major bleeding and clinically relevant non-major bleeding.

8.0 Dosage Modification Based on Adverse Events

8.1 Apixaban is cleared through several mechanisms including renal clearance, hepatic metabolism, and fecal excretion. Dalteparin is excreted through renal clearance. For both drugs, severe thrombocytopenia, liver and renal failure represents an increased bleeding risk. For these purposes, patients will require monthly assessment of complete blood counts (CBC), renal function (creatinine clearance calculation), and liver function (ALT). Each of these measures is clinically indicated for anticoagulation management.

Patients with calculated creatinine clearance ≤ 30 ml/min (using the Cockcroft-Gault formula) must discontinue treatment and go to observation. They may get alternative anticoagulation treatment per the attending physician judgment.

For patients who are receiving concomitant use of strong CYP3A4 and/or P-glycoprotein inhibitors (i.e. ketoconazole, itraconazole, ritonavir, or clarithromycin; see appendix II for a list of strong CYP3A4 inhibitors), the dose of apixaban will be reduced to 2.5 mg twice daily. Upon discontinuation of the strong CYP3A4 inhibitor, then the full dose of apixaban 5 mg twice daily should be instated/reinstated.

For patients receiving a strong CYP3A4 inducer (appendix II), alternative agents within the specific class of drug should be sought. If no good alternative agent within that class can be identified and the drug is required, the ACCRU Data Manager should be notified and the subject removed from the trial and go to observation.

For thrombocytopenia ($> 50,000$ /microliter), no dose adjustment is necessary. For

thrombocytopenia (25,000-50,000/microliter), apixaban dose reduction to 2.5 mg twice daily is necessary. For thrombocytopenia (< 25,000/microliter), apixaban will be held

until platelet count recovers. Once the platelet count improves, the apixaban dose should be adjusted accordingly.

Dalteparin therapy is weight based dosing. Monthly weights should be performed and communicated with study staff. For patients experiencing more than 10% weight loss or gain, the dose of dalteparin will be adjusted to current body weight.

The dalteparin dose should be adjusted for patients experiencing kidney injury. An exclusion criterion for study enrollment is a creatinine clearance <30 ml/min. For those patients already enrolled who then develop worsening kidney function, the dalteparin dose will then be adjusted. For creatinine clearance between 15 and 30 ml/min, the dose of dalteparin should be reduced. During the first month of treatment when the patient is receiving 200IU/kg, the dose will be reduced to 150 IU/kg. During subsequent months, the dose of 150 IU/kg will be reduced to 100 IU/kg. Once the creatinine clearance improves to values > 30 ml/min, the standard dosing will be reintroduced.

For patients with severe kidney injury defined as creatinine clearance < 15 ml/min, dalteparin should be held and the patient should stop the study treatment and receive treatment per the attending physician.

For thrombocytopenia (> 50,000/microliter), no dose adjustment is necessary. For thrombocytopenia (25,000-50,000/microliter), dalteparin dose reduction to 5000 IU/day is necessary. For thrombocytopenia (< 25,000/microliter), dalteparin will be held until platelet count recovers. Once the platelet count improves, the dalteparin dose should be adjusted accordingly.

8.2 **Patients requiring an invasive procedure requiring temporary anticoagulant cessation will be managed as follows:**

- (1) Date and type of procedure will be recorded on the CRF;
- (2) Apixaban will be discontinued at least 48 hours prior to elective surgery or invasive procedures with a moderate or high risk of bleeding, with no drug given on the procedure date; For low bleeding risk procedures, apixaban will be discontinued at least 24 hours. Dalteparin dose will be reduced to 100 IU/kg and given on the morning prior to the procedure date with no drug given on the procedure date;
- (3) Post procedure, the patient could receive prophylactic apixaban (2.5 mg twice daily) or dalteparin (5000 IU once daily) dosing for 48 hours; the first prophylactic dose will be given 24 hours after the procedure;
- (4) Therapeutic apixaban or dalteparin will be withheld until 72 hours after the procedure and not initiated until adequate hemostasis is confirmed.

If apixaban or dalteparin treatment is temporally held, the reason will be recorded on the CRF and the patient can go back on study for up to day 180 of the original treatment schedule.

9.0 **Ancillary Treatment/Supportive Care**

- 9.1 Concomitant use of strong CYP3A4 inhibitors (e.g., HIV protease inhibitors, systemic ketoconazole (appendix II) should be discouraged. In the case of clinical necessity, for

those patients randomized to apixaban, the dose of apixaban will be reduced to 2.5 mg twice daily while the CYP3A4 inhibitor is given.

- 9.2 Non-steroid anti-inflammatory drugs (NSAIDs) and antiplatelet agents (aspirin) are discouraged but not prohibited. If aspirin use is required, then the dose should be ≤ 100 mg daily. The use of these drugs should be recorded on the CRF.
- 9.3 **Note:** Antiplatelet therapy with a thienopyridine (clopidogrel, prasugrel, or ticagrelor) is an exclusion criterion and not allowed while on protocol therapy.

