3.0 Patient Eligibility

3.1 Inclusion Criteria

- 3.11 Age ≥ 18 years.
- 3.12 Confirmed acute lower extremity or upper extremity (jugular, innominate, subclavian, axillary, brachial) DVT, PE, splanchnic (hepatic, portal, splenic, mesenteric, renal, gonadal), or cerebral vein thrombosis.
- 3.13 Active cancer defined as metastatic disease and/or any evidence of cancer on cross-sectional or PET imaging, cancer related surgery, chemotherapy or radiation therapy within the past 6 months. Note: non-melanoma skin cancer does not meet the cancer requirement.
- 3.14 Life expectancy ≥ 60 days.
- 3.15 ECOG Performance Status (PS) of 0, 1, or 2. (Form is available on the ACCRU web site <https://www.ac cru.org/ac cru/forms/NonProtocolSpecificForms/index.html>).
- 3.16 The following laboratory values obtained ≤ 30 days prior to randomization.
- Platelet count $\geq 50,000/\text{mm}^3$
 - Alanine aminotransferase (ALT) or Aspartate transaminase (AST) $\leq 3 \times \text{ULN}$
 - INR ≤ 1.6 (if not taking anticoagulant therapy)
 - Calculated creatinine clearance must be ≥ 30 ml/min using the Cockcroft-Gault formula below:

Cockcroft-Gault Equation:

$$\text{Creatinine clearance for males} = \frac{(140 - \text{age})(\text{weight in kg})}{(72)(\text{serum creatinine in mg/dL})}$$

$$\text{Creatinine clearance for females} = \frac{(140 - \text{age})(\text{weight in kg})}{(72)(\text{serum creatinine in mg/dL})} * (0.85)$$

- 3.17 Negative serum or urine pregnancy test done ≤ 24 hours prior to randomization, for women of childbearing potential only.
 Note: A Women of childbearing potential (WOCBP) is defined as any female who has experienced menarche and who has not undergone surgical sterilization (hysterectomy or bilateral oophorectomy) and is not postmenopausal. Menopause is defined as 12 months of amenorrhea in a woman over age 45 years in the absence of other biological or physiological causes.
- 3.18 Ability to complete questionnaire(s) by themselves or with assistance.
- 3.19a Ability to provide informed written consent.
- 3.19b Willing to return to enrolling institution for follow-up (during the Active Monitoring Phase of the study).

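### The renal stop rule in Section 8.1 (creatinine clearance ≤ 30 ml/min) names no arm and, read literally, contradicts the dalteparin rule that continues treatment at 15–30 ml/min on a reduced dose

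*Combined protocol and SAP*

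**What the plan says.** Section 8.1 opens with a paragraph on how each drug is cleared and on monthly laboratory checks. It includes the statement "For both drugs, severe thrombocytopenia, liver and renal failure represents an increased bleeding risk". The next paragraph gives the stop rule: "Patients with calculated creatinine clearance ≤ 30 ml/min (using the Cockcroft-Gault formula) must discontinue treatment and go to observation". It adds that such patients may receive another anticoagulant at the attending physician's discretion.

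Further on, after the weight-based dosing paragraph, the section gives a separate renal rule for enrolled dalteparin patients whose kidney function worsens:

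- "For creatinine clearance between 15 and 30 ml/min, the dose of dalteparin should be reduced". The reduction is from 200 to 150 IU/kg in month 1 and from 150 to 100 IU/kg afterwards.
- The patient returns to the standard dose when clearance recovers to above 30 ml/min.
- "For patients with severe kidney injury defined as creatinine clearance < 15 ml/min, dalteparin should be held", with study treatment stopped and care passed to the attending physician.

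Eligibility (Section 3.16) reads: "Calculated creatinine clearance must be ≥ 30 ml/min using the Cockcroft-Gault formula below".

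**The concern.** The stop rule applies to patients without qualification and is worded as mandatory. The dalteparin rule gives the opposite instruction for part of the same range, and no sentence ranks the two. A site that follows the stop rule takes a dalteparin patient at 22 ml/min off study treatment. A site that follows the dalteparin rule keeps that patient on a reduced dose and restores the standard dose on recovery. Each site can point to the protocol.

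The instruction concerns an anticoagulant that Section 15.26 describes as mainly renally excreted, in patients whom Section 8.1 itself places at raised bleeding risk. Section 1.1 notes that renal failure can be common in cancer, and clearance is checked monthly, so the situation is foreseeable. What is at stake is patient safety and consistent treatment across sites.

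**Working it through.** The plan states no figure on this point, so the check sets the two rules side by side for a patient on dalteparin.

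| Creatinine clearance (ml/min) | Stop rule, read literally | Dalteparin rule | Agreement |
|---|---|---|---|
| Above 30 | Does not apply | Standard dose | Yes |
| 15 to 30 | Stop study treatment, go to observation | Continue at reduced dose | **Opposite** |
| Below 15 | Stop study treatment | Stop study treatment | Yes |

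If the stop rule covered both arms, no dalteparin patient could reach the 15–30 reduction or the return to standard dose, and the separate stop below 15 would be redundant. If it covers apixaban only, every sentence has work to do.

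**How wide the range is in practice.** This is one assumed patient, not a trial estimate: a man aged 80 weighing 72 kg. The protocol's Cockcroft-Gault formula for males is (140 − age) × weight / (72 × creatinine). Here it gives (60 × 72) / (72 × creatinine) = 60 / creatinine.

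- Creatinine 2.0 mg/dL: 60 / 2.0 = 30.0 ml/min
- Creatinine 2.7 mg/dL: 60 / 2.7 = 22.2 ml/min
- Creatinine 4.0 mg/dL: 60 / 4.0 = 15.0 ml/min

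For this man the rules conflict at every creatinine value from 2.0 to 4.0 mg/dL. At 22.2 ml/min in months 2–6, the dalteparin rule gives 100 × 72 = 7,200 IU/day (unrounded, because Table 7.11 has no 100 IU/kg column). The literal stop rule gives no study drug, with alternative anticoagulation left to the physician. The dose reduction itself is what the protocol intends and does not measure the defect.

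**Boundary at 30.** Eligibility is ≥ 30 and the stop rule is ≤ 30, so the two overlap at exactly 30. The man above with creatinine 2.0 mg/dL could be enrolled at 30.0 and would meet the stop rule if his next monthly value were unchanged. Return to standard dalteparin dosing requires a value above 30.

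**The case against.** The best answer is that the section read as a whole settles the scope. After the introduction, Section 8.1 runs through apixaban (renal function, CYP3A4 inhibitors, CYP3A4 inducers, platelets) and then dalteparin (weight, renal function, platelets). The platelet steps are written out twice, once per drug, which makes sense only if the section is arranged by drug. The dalteparin renal text is specific to enrolled patients with worsening kidney function, and a specific rule normally governs over a general one. Other sentences in the apixaban run, such as the inducer paragraph and the first platelet sentence, also name no drug, so the omission looks like drafting habit. The paragraph about both drugs introduces the whole section, so its position directly before the stop rule says little about that rule's scope.

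Most of this stands, and it makes an apixaban-only intent probable. It does not remove the literal contradiction in a mandatory rule. The unqualified platelet sentence is harmless because the dalteparin run repeats the same instruction, whereas the two renal instructions are opposed. A both-arms stop is also clinically plausible on the document's own account. Section 1.1 says renal failure limits use of low molecular weight heparin, and Section 1.2 puts renal excretion at only about 27% of apixaban clearance. The apixaban-only reading therefore places the stricter stop on the less renally cleared drug. That may be deliberate, but a site could not be sure of it. Section 9.1 shows that the protocol can name the arm when it wants to: "those patients randomized to apixaban, the dose of apixaban will be reduced to 2.5 mg twice daily". This is weak evidence, since the two sections differ in style, but it is a ready model for the correction.

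A reader might also infer that the stop rule leaves patients without anticoagulation. It does not, because the sentence after it allows alternative treatment.

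**Conclusion.** The point holds as a contradiction in wording: from 15 to 30 ml/min, Section 8.1 gives a dalteparin patient two opposing instructions. The probable intent is a stop for apixaban only, but that rests on layout and on giving effect to the dalteparin text, not on any statement of scope. It should be fixed because it is a mandatory dosing instruction and the correction costs almost nothing.

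The documents do not say how many patients would fall in this range, so no trial-wide size can be given. A reader might infer that the primary result is biased, because Section 16.21 focuses on bleeds during treatment or within 7 days of stopping, and the reading chosen changes when dalteparin treatment stops. The documents do not support that inference. They give neither the number of such patients nor their bleeding rates, and Section 16.22 plans an intent-to-treat sensitivity analysis that covers part of the issue. A reader might also infer that the clearance thresholds are clinically wrong. Nothing in the documents shows this.

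The overlap at exactly 30 is real but minor, since it concerns a single value of a calculated estimate.

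**What to change.** In the stop rule of Section 8.1, insert *allocated to apixaban* after the opening word and leave the ≤ 30 threshold as it stands. Send sites a notice stating that dalteparin patients follow the dalteparin renal rule. If the sponsor's clinicians intended the stop for both arms, write *in either arm* instead and delete the dalteparin text on the 15–30 reduction, the return to standard dose and the stop below 15.

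Either route needs a short wording change in one section and a site notice. It does not touch the analysis, sample size or visit schedule.

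Separately, the sponsor's clinicians should make the eligibility and stop boundaries consistent at exactly 30. Either boundary can move. The direction is a clinical choice and need not delay the scope correction.

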- a) Absorption – Time to peak after oral administration is 3 to 4 hours; bioavailability is approximately 50% for doses up to 10 mg.

- b) Distribution – Plasma protein binding in humans is approximately 87%. The steady-state volume of distribution is approximately 21 L.
 - c) Metabolism – Approximately 25% of an orally administered apixaban dose is recovered in urine and feces as metabolites. Apixaban is metabolized mainly via CYP3A4 and to a lesser extent via CYP1A2, 2C8, 2C9, 2C19, and 2J2
 - d) Excretion Apixaban is eliminated in both urine and feces. Renal excretion accounts for about 27% of total clearance.
 - e) Half-life Elimination – approximately 12 hours
- 15.17 Drug interactions: Apixaban is a substrate of both CYP3A4 and P-gp. Inhibitors of CYP3A4 and P-gp increase exposure to apixaban and increase the risk of bleeding. Inducers of CYP3A4 and P-gp decrease exposure to apixaban and increase the risk of stroke

Strong Dual Inhibitors of CYP3 A4 and P-gp

The dose of ELIQUIS should be decreased to 2.5 mg twice daily when is coadministered with drugs that are strong dual inhibitors of CYP3A4 and P-gp. (e.g.; ketoconazole, itraconazole, ritonavir, or clarithromycin).

In patients already taking ELIQUIS at a dose of 2.5 mg twice daily, avoid coadministration with strong dual inhibitors of both CYP3A4 and P-gp.

Strong Dual Inducers of CYP3A4 and P-gp

Avoid concomitant use of ELIQUIS with strong dual inducers of CYP3A4 and P-gp (e.g. e.g., rifampin, carbamazepine, phenytoin, St. John's wort) because such drugs will decrease exposure to apixaban.

Coadministration of antiplatelet agents, fibrinolytics, heparin, aspirin, and chronic NSAID use increases the risk of bleeding.

Please consult current drug reference sources for a complete list of potential drug interactions.

- 15.18 Please consult the package insert for the most current and complete adverse event information.
- 15.19a Drug procurement: Bristol Myers-Squibb will supply the drug to Biologics, Inc. Each participating ACCRU treating location will order the drug from Biologics, Inc. Fax the Drug Order Request Form (found in the forms packet) to:
- Biologics, Inc.
 - Attn. Clinical Research Services
 - Fax: [REDACTED]

Each participating ACCRU treating location will be responsible for monitoring the supply of apixaban and will use the Drug Order Request Form to order additional supplies as needed.

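### Sections 8.1, 9.1 and 15.17 define the interacting drug that triggers apixaban 2.5 mg twice daily in three different ways, so dosing instructions diverge for inhibitors that are not dual CYP3A4 and P-gp inhibitors

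*Combined protocol and SAP*

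**What the plan says.** Three sections order the same action, a reduction to 2.5 mg twice daily, for differently defined drugs.

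- **Section 8.1 (dosage modification).** The trigger is "concomitant use of strong CYP3A4 and/or P-glycoprotein inhibitors". The parenthesis that follows reads "i.e. ketoconazole, itraconazole, ritonavir, or clarithromycin; see appendix II for a list of strong CYP3A4 inhibitors". The return rule is "Upon discontinuation of the strong CYP3A4 inhibitor, then the full dose of apixaban 5 mg twice daily should be instated/reinstated".
- **Section 9.1 (ancillary treatment).** "Concomitant use of strong CYP3A4 inhibitors (e.g., HIV protease inhibitors, systemic ketoconazole (appendix II) should be discouraged". If such a drug is clinically necessary, "the dose of apixaban will be reduced to 2.5 mg twice daily while the CYP3A4 inhibitor is given". P-gp is not mentioned.
- **Section 15.17 (apixaban drug interactions).** "The dose of ELIQUIS should be decreased to 2.5 mg twice daily" when apixaban is given with "drugs that are strong dual inhibitors of CYP3A4 and P-gp". The examples are the same four drugs that 8.1 names.

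The unmodified schedule in section 7.1 is 10 mg twice daily on days 1-7 and 5 mg twice daily on days 8-180. No section says which of the three definitions governs if they differ.

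**The concern.** The three definitions are not paraphrases of one another. On its literal wording 8.1 is met by either property, 9.1 by the CYP3A4 property alone, and 15.17 only by both together. Staff who look up the rule in different places can therefore reach different doses for the same patient while each follows the protocol as written.

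Only the apixaban arm is exposed to this. The primary safety analysis (section 16.21) groups patients by drug received and focuses on bleeding during treatment or within 7 days of stopping, so time at a reduced dose counts as apixaban time. Uneven application of the rule would make the apixaban regimen under study vary between sites for a reason the protocol did not intend. For the individual patient, the instructions contradict one another.

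**Working it through.** The plan states no figure on this point to reproduce. The check sets the three triggers side by side for each type of interacting drug.

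| Interacting drug | 8.1, literal wording | 8.1, four named drugs as a closed list | 9.1 | 15.17 |
|---|---|---|---|---|
| Strong dual CYP3A4 and P-gp inhibitor | 2.5 mg | 2.5 mg if one of the four | 2.5 mg | 2.5 mg |
| Strong CYP3A4 inhibitor, not dual | 2.5 mg | not triggered by the list | 2.5 mg | not triggered |
| P-gp inhibitor, not a strong CYP3A4 inhibitor | 2.5 mg | not triggered by the list | not triggered | not triggered |

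All doses are twice daily. Where a trigger is not met, the section 7.1 schedule stands.

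**Row 1.** On the literal wording there is no conflict over the reduction. For the four drugs named in both 8.1 and 15.17, every section gives 2.5 mg.

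**Row 2.** This is the firmest divergence. The wording of 8.1 and its pointer to appendix II, described there as a CYP3A4 list, lead to 2.5 mg, as does 9.1. The trigger in 15.17 is not met. If the four drugs in 8.1 are read as a closed list, 8.1 drops out, but 9.1 still differs from 15.17.

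**Row 3.** This divergence rests on the *and/or* in 8.1 alone. The return rule in 8.1 mentions only the strong CYP3A4 inhibitor, so on the literal reading the entry and exit conditions of one rule do not match.

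**Size of the dose difference where the sections diverge**
- Days 8-180: 5 mg against 2.5 mg twice daily, 5 / 2.5 = a factor of 2.
- Days 1-7: 10 mg against 2.5 mg twice daily, 10 / 2.5 = a factor of 4. None of the three sections treats these days separately, so describing the rule as halving the dose fits days 8-180 only.

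**What cannot be worked out.** Appendix II is not in the text available for review, so the number of non-dual drugs it lists is unknown. The documents do not say how many patients would take such a drug, so no count of affected patients can be derived.

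**A neighbouring mismatch.** Section 15.17 adds: "In patients already taking ELIQUIS at a dose of 2.5 mg twice daily, avoid coadministration with strong dual inhibitors of both CYP3A4 and P-gp". Section 8.1 places apixaban patients with platelets of 25,000-50,000/microliter on 2.5 mg twice daily, yet neither 8.1 nor 9.1 carries this provision. It can be reconciled in the same edit.

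**The case against.** The strongest reply is that the protocol is more coherent than the *and/or* suggests. Section 8.1 introduces its four drugs as a restatement, they are the same four that 15.17 gives as dual inhibitors, the appendix pointer concerns CYP3A4, and so does the return rule. Read as a whole, 8.1 is about strong CYP3A4 inhibitors, as is 9.1. Section 15.17 sits under drug information, uses the brand name and says nothing on non-dual inhibitors. In addition, 9.1 discourages these drugs and allows them only where clinically necessary, so such cases may be few.

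Much of this stands, and it rules out several stronger readings that a reader might infer:

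- *That 15.17 forbids the reduction for a non-dual inhibitor.* It does not. The scheduled dose follows only because its trigger is unmet.
- *That a patient reduced for a P-gp-only drug would stay on 2.5 mg to day 180 with no way back.* This depends on *and/or* read apart from the rest of 8.1. No section names a P-gp-only drug as a trigger.
- *That time at the lower dose would reduce major bleeding and raise VTE recurrence on apixaban.* Section 15.17 itself says that inhibitors of CYP3A4 and P-gp raise apixaban exposure and bleeding risk. The lower dose is given alongside the inhibitor, so the net exposure, and the direction of any effect, is not established.

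The reply does not remove the inconsistency. Section 9.1 reaches a CYP3A4 class, with HIV protease inhibitors named as a group, that the wording of 15.17 does not. Section 15.17 is still protocol text that gives a dosing instruction. Appendix II, as 8.1 describes it, is not a list of dual inhibitors, and no section is given precedence.

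**Conclusion.** The point holds as an inconsistency in dosing instructions. The trigger for 2.5 mg twice daily is worded three ways. The sections agree for the four named dual inhibitors, and 9.1 (with 8.1 on its literal wording) diverges from 15.17 for strong CYP3A4 inhibitors that are not dual. The P-gp-only divergence is real on the literal text of 8.1 but weaker, because the rest of that paragraph points to CYP3A4.

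Where the sections diverge, the dose differs by a factor of 2 on days 8-180 and 4 on days 1-7. This rests on two assumptions: that an unmet trigger leaves the section 7.1 schedule in force, and that at least some patients take a non-dual inhibitor. The documents do not allow the second to be checked.

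A reader might go further and infer a bias in the primary comparison of major bleeding. The documents do not support that, since they give neither the number of patients nor the direction of effect. The text should be corrected because patients and sites need one instruction, not because an effect on the result has been shown. Which class is clinically right is not judged here.

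**What to change.** Reconcile 8.1, 9.1, 15.17 and appendix II to a single trigger class. The sponsor's clinical team should choose the class. Then:

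- use identical wording in all four places, and state whether the named drugs are examples or a complete list;
- key the return rule in 8.1 to stopping any drug in that same class;
- state how the rule applies on days 1-7, and carry or cross-refer to the 15.17 provision for patients already on 2.5 mg, as the clinical team decides;
- confirm that the existing forms capture start and stop dates of the triggering drug and of any reduced-dose period. Selected concomitant medications are already collected at baseline and every 30 days (section 4.0), and section 18.1 lists a concomitant-medication form and arm-specific evaluation/treatment forms. Their fields are not shown, so this may need no change.

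The cost is a short amendment to a few sentences and the appendix, and possibly a form check. It needs no extra patients, visits or procedures.
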